 - b. For a Reference Glucose Value of 54-69 mg/dL with accompanying symptoms of hypoglycemia – anxiety, irritability, sweating, hunger, shakiness, fatigue, pale skin, lethargy, seizures.
 - c. For any Reference Glucose Value when the subject is experiencing signs of hypoglycemia caused by a rapid fall in the subject's blood glucose level (e.g., neuroglycopenia) and the ingestion of snacks or glucose containing juices do not relieve these symptoms within 10 minutes from the time the snacks/juice is ingested.
3. If intravenous access is no longer available and the subject has a Reference Glucose Value less than 70 mg/dL, or is exhibiting signs of neuroglycopenia, the subject will be given Glucagon 1 mg intramuscularly every 15 minutes as needed until their Reference Glucose Value is greater than 70 mg/dL on two consecutive checks that are separated in time by at least 30 minutes, and when their hypoglycemia symptoms have completely resolved.

The other potential risks of participating in this study include severe hyperglycemia, diabetic ketoacidosis, hyperosmolar hyperglycemic syndrome, excessive blood removal (lab draws), and fluid overload.

Given the FUSION systems results in its first in human testing, the current studies proposed control range of 100-140 mg/dL, and the above monitoring and risk mitigation strategies, no alternative procedures are warranted at this time.

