8.5.1 RESCUE MEDICINE

The study site will supply rescue medication that will be obtained locally. The following rescue medications may be used:

1. 15 mL of 50% Dextrose for intravenous delivery (IV push), every 10 minutes as needed.
2. Glucagon (1 mg/mL) for Intramuscular or intravenous delivery. May give repeat dose 15 minutes after first dose.

The 50% dextrose and Glucagon rescue medications will be used to treat the following conditions:

- 1) Severe hypoglycemia, which is defined as a Reference Glucose Value less than 54 mg/dL.
- 2) Moderate hypoglycemia (Reference Glucose Value in the range of 54-69 mg/dL) that is accompanied by any of the following neurological signs of hypoglycemia: Anxiety, irritability, sweating, hunger, shakiness, fatigue, pale skin, lethargy, seizures.
- 3) Neuroglycopenia, which is defined as hypoglycemia of sufficient duration and degree to interfere with normal brain metabolism and function. Neuroglycopenia may occur at Reference Glucose Values greater than or equal to 70 mg/dL. If the subject has signs of hypoglycemia such as anxiety, irritability, sweating, hunger, shakiness, fatigue, pale skin, lethargy, or seizures, they will be treated with 15 mL of 50% Dextrose."

These medications will be hand pushed into the subject's intravenous line by the study nurse or given by intramuscular injection in the case of Glucagon. The date and time of rescue medication administration as well as the name and dosage regimen of the rescue medication will be recorded on the case report forms.

In addition to the above rescue medications, in cases of severe hypoglycemia, moderate hypoglycemia with hypoglycemia symptoms, or neuroglycopenia, the subjects will also be offered snacks and glucose containing juices to treat their hypoglycemia and related symptoms.

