DEMONSTRATION OF AN ARTIFICIAL INTELLIGENCE BASED CLOSED LOOP GLUCOSE CONTROL SYSTEM AS A THERAPEUTIC MODALITY IN TYPE 1 AND TYPE 2 DIABETIC PATIENTS

Protocol IMT 2022-1

CONFIDENTIAL

Version1.0.7

[figure not shown]
22 August 2022

To avoid risk to our human subjects, vital signs will be monitored closely. Frequent independent glucose measurements will be performed (every 10-60 minutes) to minimize the risk of severe hypoglycemia (< 54 mg/dL) or moderate hypoglycemia (54-69 mg/dL) with the above noted hypoglycemia symptoms. The protocol calls for rescue doses of 15 mL of 50% dextrose for severe hypoglycemia, moderate hypoglycemia with hypoglycemia symptoms, or neuroglycopenia. In addition, the study on any one subject will be terminated if they experience a severe hypoglycemia event (< 54 mg/dL). The overall study will be terminated if two subjects experience a severe hypoglycemia event (< 54 mg/dL).

Patients with a history of liver failure, renal failure, cerebrovascular accident, seizure disorder, congestive heart failure, and ischemic heart disease will not be recruited for this study.

During the time period when the FUSION system is operational and active, if a participant's CGM or Reference Glucose Value is >240 mg/dL for over 1 hour or ≥ 300 mg/dL at any point after starting the FUSION system, the following steps will be taken: Ketones will be assessed at the discretion of the principal investigator(s) for any concern about possible ketosis or DKA by checking a blood ketone level at the bedside. If the blood ketone level is greater than 1 mmol/L, a venous blood sample from the subject will be sent to the central laboratory of Emory Healthcare for a basic metabolic panel, blood pH, and beta hydroxybutyrate level. If the subject is found to be in DKA, the subject will be stabilized per the usual routine care at Emory Healthcare.

When a hyperglycemia/ketotic event meets the above reporting requirements, an Adverse Event Form will be completed. Events meeting DKA criteria should be considered serious adverse events with respect to reporting requirements. Hyperglycemia events not meeting criteria for DKA generally will not be considered as serious adverse events unless one of the severe adverse event criteria is met.

| Meal Challenge Protocol Detailed | | | | | | | | | |
|--|---|------|-----------------------------|-----------|----|-------|----|--------|----|

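### Sections 4.1 and 8.5.1 give incompatible rules for rescue dextrose in neuroglycopenia, and their glucagon wording is not aligned

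*Combined protocol and SAP*

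**What the plan says.** **Dextrose.** Section 4.1 lists three situations for a rescue dose of 15 mL of 50% dextrose: a Reference Glucose Value below 54 mg/dL (2a), a value of 54-69 mg/dL with symptoms (2b), and signs at any value attributed to a rapid fall (2c). Item 2c carries a further condition: "the ingestion of snacks or glucose containing juices do not relieve these symptoms within 10 minutes".

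Section 8.5.1 names the same three kinds of event. For neuroglycopenia, which it says may occur at 70 mg/dL or above, it lists the signs and then instructs: "shakiness, fatigue, pale skin, lethargy, or seizures, they will be treated with 15 mL of 50% Dextrose". Oral treatment comes on top of the medication: "the subjects will also be offered snacks and glucose containing juices to treat their hypoglycemia and related symptoms".

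Protocol 2, under Potential Problems, restates the rule without an oral-first step: "The protocol calls for rescue doses of 15 mL of 50% dextrose for severe hypoglycemia, moderate hypoglycemia with hypoglycemia symptoms, or neuroglycopenia". Section 4.3.2 also mentions rescue dextrose for neuroglycopenia without that condition.

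**Glucagon.** Section 4.1 item 3 covers loss of intravenous access with a Reference value below 70 mg/dL or signs of neuroglycopenia: "the subject will be given Glucagon 1 mg intramuscularly every 15 minutes as needed until their Reference Glucose Value" exceeds 70 mg/dL on two consecutive checks at least 30 minutes apart and symptoms have resolved. Section 8.5.1 allows the intramuscular or intravenous route and adds: "May give repeat dose 15 minutes after first dose". It gives no endpoint for stopping.

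**Analysis.** Section 11.4.4 reports the percentage of subjects needing rescue medicine, identified as use according to 8.5.1.

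**The concern.** Section 4.1 names hypoglycemia as the main risk of tight glucose control, and these are the instructions staff would use when a subject becomes symptomatic. Both dextrose texts are current and both are worded as instructions. One makes the dose depend on a failed 10-minute trial of oral treatment, and the other does not. A nurse cannot comply with both, and whichever is followed can be recorded as a deviation from the other.

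There is also a reporting consequence. A subject whose signs clear with juice inside 10 minutes receives no rescue medicine under 4.1 but does receive it under 8.5.1. The rate in 11.4.4 then depends partly on which section the bedside staff had read.

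**Working it through.** The documents state no figure on this point, so the check is a side-by-side reading. The inputs are section 4.1 (lead-in and items 1-3), section 8.5.1, Protocol 2 (Potential Problems), section 11.4.4, and the sample size of eight in section 11.2.

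**Step 1. Dextrose by Reference Glucose Value.**

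| Situation | Section 4.1 | Section 8.5.1 |
|---|---|---|
| Below 54 mg/dL | Dextrose (2a) | Rescue condition |
| 54-69 mg/dL with symptoms | Dextrose (2b) | Rescue condition |
| 54-69 mg/dL, no symptoms | Not listed | Not listed |
| 70 mg/dL or above, with signs | Dextrose only after oral treatment has failed for 10 minutes (2c) | Dextrose on signs; oral treatment offered as well |

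The dose is the same throughout. The first three rows agree. Because any one of 2a, 2b or 2c suffices under 4.1, a symptomatic subject at 54-69 mg/dL already qualifies through 2b without a wait. The conflict is therefore confined to the last row.

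**Step 2. Can both rules be followed in the last row?** Take a subject with shakiness and sweating at 75 mg/dL. Under 4.1 the subject takes juice and is observed, and if the signs clear within 10 minutes no dextrose is given. Under 8.5.1 the signs alone call for dextrose. No single action satisfies both. Protocol 2 does not settle it, because it lists neuroglycopenia as a trigger and says nothing about oral treatment first.

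**Step 3. Weight in the rescue summary.** If all eight subjects start closed-loop control, one subject whose rescue status turns on the rule moves the rate by 1/8 = 0.125, or 12.5 percentage points. This is the granularity of any yes/no outcome in eight subjects. It is not an estimate of how many would be affected.

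**Step 4. Glucagon.**

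| Element | Section 4.1 item 3 | Section 8.5.1 | Compatible? |
|---|---|---|---|
| Trigger | Any value below 70 mg/dL, or neuroglycopenia, once access is lost | Below 54; 54-69 with symptoms; neuroglycopenia | Item 3 is broader as worded |
| Route | Intramuscular | Intramuscular or intravenous | Yes; intramuscular satisfies both |
| Interval | 15 minutes | 15 minutes | Yes |
| Stopping | Two values above 70 mg/dL at least 30 minutes apart, symptoms resolved | None stated | Not aligned |

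Item 3 is also broader than its own lead-in. That lead-in introduces items 1-3 as treatment for a value below 54 mg/dL, a value of 54-69 mg/dL with symptoms, or neuroglycopenia. Symptoms are required at 54-69 mg/dL in the lead-in and in 8.5.1, but not in item 3.

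**The case against.** **Section 4.1 is background and 8.5.1 governs.** Section 4.1 is a risk section, but it is written as instructions, down to dose, interval and stopping rule. Nothing in it defers to 8.5.1, so a reader has no stated order of precedence.

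**Section 8.5.1 is permissive, so 4.1 only adds detail.** The list of medications is introduced as what may be used, and that has force for glucagon. It does not help with dextrose, where the neuroglycopenia sentence is an instruction to treat. Added detail cannot turn an immediate dose into one that waits for oral treatment to fail.

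**The glucagon rules contradict each other on every element.** A reader might infer that an asymptomatic subject at 60 mg/dL without a line gets glucagon under 4.1 and not under 8.5.1. Item 3 taken alone says so, but under the lead-in that subject does not enter the list at all. The discrepancy lies first within 4.1. A reader might also infer that 4.1 restricts glucagon to loss of access. It says what is done in that case and does not exclude others. Route and interval can be met under both sections, so what stands is the trigger wording and the missing endpoint.

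**The primary endpoints are affected.** A reader might infer this because dextrose changes later glucose values. The documents do not support a claim of any size. The endpoints use the controller's glucose data while the controller is in use. The controller acts through an intravenous line, so the no-access glucagon case hardly reaches them. Below 54 mg/dL the sections agree on dextrose, and the subject is terminated under 9.1 in any case. What is left is a delay of up to 10 minutes, or a dose avoided, in an unknown and possibly very small number of subjects.

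**Conclusion.** The dextrose conflict is real. For signs of neuroglycopenia at a Reference value of 70 mg/dL or above, section 4.1 requires 10 minutes of failed oral treatment before the dose, and 8.5.1 does not. Protocol 2 states no oral-first step. Both rules cannot be followed at the bedside.

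The glucagon point is secondary. Item 3 of 4.1 is worded more broadly than its lead-in and than 8.5.1, and the two sections differ on whether there is a dosing endpoint. This calls for alignment of wording; it does not show that the glucagon rules exclude each other.

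On size, one subject in eight is 12.5 points of a descriptive rescue rate that 11.4.4 ties to 8.5.1. This assumes that all eight subjects start closed-loop control. How many would meet the conflicting situation is unknown. Section 4.1 reports no time below 70 mg/dL in the two earlier subjects, but the conflict concerns signs at or above 70 mg/dL, so that result says little about it. No effect on the primary endpoints is claimed. The case for correction rests on having one rule for symptomatic subjects and a clear rescue count. No view is taken on which rule is clinically right.

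**What to change.** The passages must be reconciled. Put one rescue rule in 8.5.1, preferably as a table, that gives for dextrose and for glucagon the trigger, the order relative to oral treatment, the route, the repeat rule and the stopping rule. Replace the rescue instructions in 4.1, 4.3.2 and Protocol 2 with a reference to it. In doing so, settle whether the glucagon trigger follows the lead-in of 4.1 or the wording of item 3. The investigators should choose the content. Section 11.4.4 can keep its reference to 8.5.1, and once there is a single rule, every rescue dose given under the protocol has a place in that summary.

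The cost is protocol wording, with the IRB approval that the Statement of Compliance requires for any amendment. Sample size, endpoints and data collection do not change.

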4.2 KNOWN POTENTIAL BENEFITS

The immediate benefits for participants with diabetes in a brief (31 hour) tight glucose control study in a CRC setting are limited. However, development of a closed loop glucose control system designed for use in the inpatient setting may have long term benefits for this patient population, as preliminary studies have demonstrated improved outcomes through use of automated closed loop glucose control in this group in the non-ICU inpatient setting.^{85,86}

With regards to benefits to ICU patients, as has been previously noted, effective tight glucose control can lead to decreased morbidity rates, whether it be decreased wound infection rates in post-operative patients,⁷² or decreased renal failure and blood transfusions rates.⁶ In addition, mortality rates will be lower if the subject is able to maintain a high time in the control range,¹⁶ while at the same time avoiding any hypoglycemia events.¹⁴ Finally, safe and effective tight glucose control has the potential to lower critical illness related mortality including COVID-19 related mortality.³⁵

Long term potential benefits for the ICU patient population mainly relate to a shorter overall recovery period based on decreased complication rates and the potential for a shorter ICU length of stay to decrease mortality rates after hospital discharge.⁸⁷

4.3 ASSESSMENT OF POTENTIAL RISKS AND BENEFITS

4.3.1 FAILURE OF DEXCOM G6 CONTINUOUS GLUCOSE MONITOR(S)

The risk of complete failure of the continuous glucose monitoring system will be mitigated through use of two Dexcom G6 CGM systems, which will provide redundancy to this critical component of the FUSION artificial pancreas system. In addition, replacement of the Dexcom CGM system – sensor, transmitter, or receiver – will be allowed if any of these three components of an individual CGM system experiences a failure. To clarify, the FUSION system uses a simple average of the two Dexcom G6 CGM values to decide what steps to take to bring the subject's blood glucose value into the desired control range. In order to be averaged, these two Dexcom G6 CGM values must be time stamped within 5 minutes of each other. The FUSION system will operate for up to four hours with glucose readings from only one Dexcom G6 CGM system, and for up to 20 minutes with no values from either Dexcom G6 CGM

DEMONSTRATION OF AN ARTIFICIAL INTELLIGENCE BASED CLOSED LOOP GLUCOSE CONTROL SYSTEM AS A THERAPEUTIC MODALITY IN TYPE 1 AND TYPE 2 DIABETIC PATIENTS

Protocol IMT 2022-1

CONFIDENTIAL

Version1.0.7

22 August 2022

system. The FUSION system will automatically shut down after four hours if it has only one Dexcom G6 CGM system available for use. The FUSION system will automatically shut down if it has no Dexcom G6 CGM systems available for use for a period of time exceeding 20 minutes.

The Dexcom G6 CGM Sensor/Transmitter pair communicate via Bluetooth, to the Dexcom G6 Receiver. IMT has not altered in any way, how the Dexcom G6 CGM system works or handles communications between the Transmitter and Receiver. The Dexcom G6 CGM system sends new glucose values to the Receiver every 5 minutes, if they are available, from the Sensor/Transmitter pair attached to the subject. The Dexcom G6 CGM manual notes that the Transmitter and Receiver must be within 20 feet of each other, with no obstacles between them (e.g., walls) in order to effectively communicate via Bluetooth. The FDA is aware of the 20 foot range limitation of the Dexcom G6 CGM system and has approved this CGM system for use in artificial pancreas systems. IMT has developed software called a Driver, that queries the database of the Dexcom G6 Receiver, every 30 seconds, for new glucose values. When the Driver discovers new date/time stamped glucose values in the database of the Receiver, it brings these values into a glucose queue within the FUSION system for use by the FUSION system. The FUSION system will only average glucose values that are time stamped within 5 minutes of each other. The all-in-one Medical Computer running the FUSION systems software is connected to the Dexcom G6 CGM Receiver via a serial data cable. In our internal testing, each Dexcom G6 CGM Receiver was able to receive new glucose values from the Dexcom G6 Transmitter 99.53% of the time within the designed 5 minute time interval.

The benefit of using the Dexcom G6 CGM is that the FDA has already approved this system for use as an integrated continuous glucose monitor (iCGM) in automated insulin dosing (AID) systems for use in treatment of patients with diabetes in the outpatient setting. This study and follow-up studies to be performed in the ICU setting will attempt to demonstrate the feasibility of using the Dexcom G6 CGM system in an AID system (e.g., FUSION) designed for use in the inpatient setting.

In addition, the study will also demonstrate the ability of the Dexcom G6 transmitter to simultaneously transmit its glucose data to one medical device (e.g., the Dexcom G6 Receiver) and the Dexcom G6 Follow App on a mobile phone placed 15 feet from the subject's bed. Demonstration of this functionality is important, as a mobile phone device will be needed in the ICU setting to provide remote monitoring (e.g., outside of the room) of the subject's continuous glucose measurements.

4.3.2 USE OF INNACURATE CGM GLUCOSE VALUE FOR GLUCOSE CONTROL

The risk of using an inaccurate CGM value for glucose control will be mitigated by averaging the glucose value of the two CGM devices. In addition, independent Reference Glucose Values (Nova StatStrip Hospital Glucose Meter System) will be obtained every 10-60 minutes to ensure subject safety.

The benefit of using Dexcom's G6 CGM, which has already been approved as an iCGM, is to determine its accuracy in different scenarios/settings (e.g., participants with diabetes in the proposed study; COVID-19 patients in ICU in future study).

The benefit of obtaining Reference Glucose Values every 10-60 minutes is to independently monitor for hypoglycemia in cases where the CGM systems are providing the FUSION system with false high glucose levels that could lead to hypoglycemia, or to monitor for hyperglycemia in cases where the CGM systems are providing the FUSION system with false low glucose levels that could lead to hyperglycemia. The Reference Glucose Values can be used to administer rescue doses of 50% intravenous dextrose in cases of severe hypoglycemia (< 54 mg/dL), moderate hypoglycemia (54-69 mg/dL) with associated hypoglycemia symptoms, or in cases of neuroglycopenia.

4.3.3 USE OF FALSE LOW CGM VALUES DUE TO COMPRESSION OF SENSOR SITE

The risk of using a CGM value that is falsely low due to local compression of the sensor site, due to the subject laying on the sensor site, will be mitigated by monitoring of the Dexcom G6 CGM values by the study nurse. When the study nurse notes the presence of a compression artifact, which manifests as a sudden non-physiologic fall in the glucose value (e.g., $< \pm 2$ mg/dL/min), the study nurse will move the subject until they are no longer laying on the sensor site. If one of the two abdominal sensors experiences repeated compression artifact values, the study nurse will have the option of placing a new CGM sensor on an alternative abdominal site, or on the posterior aspect of the contralateral upper arm from the abdominal sensor that continues to function normally (e.g., right side of abdomen and posterior aspect of left upper arm). The arm position may decrease the risk of both sensors suffering from compression artifacts, which could occur if the subject were to lay on both of their abdominal sensors during sleep.

A recent study involving the Dexcom G7 CGM revealed that positioning the CGM on the back of the upper arm was as accurate and reliable as the abdominal position.⁸⁸ This study, which involved 316 participants and 77,774 paired (CGM vs YSI) glucose values, demonstrated an overall MARD of 8.2% for the arm and 9.1% for the abdomen. Among the 308 sensors worn on the arm, 291 (94.5%) had >80% of CGM-YSI matched pairs that met the %20/20 accuracy criterion. Among the 311 sensors worn on the abdomen, 272 (87.5%) had >80% of matched pairs that met the %20/20 accuracy criterion. There were no serious adverse events in the study population.

The benefit of using the arm position will be to demonstrate its potential utility in a closed loop glucose control system, and to demonstrate its accuracy relative to the abdominal position as measured against the Reference Glucose Value.

4.3.4 EXCESSIVE VOLUME LOADING FROM FUSION SYSTEM

In the first in human study performed on two subjects with type 2 diabetes in the CRC, the FUSION system infused an average of 26% of the subject's total daily volume needs during the 24 hour study period. The risks to the subjects from this amount of volume include generalized edema in the setting of abnormal renal/liver function, or exacerbation of underlying congestive heart failure in the setting of underlying congestive heart failure. This risk will be mitigated by selecting subjects who have no underlying renal, liver, or cardiac conditions.

This risk will also be mitigated by further optimizing the FUSION systems glucose control software, based on an analysis of the results from the first two subjects studied. These optimization efforts include steps to prevent excessive use of insulin during states of hyperglycemia (e.g., > 140 mg/dL), which can lead to a rapid fall of elevated glucose values into and through the desired glucose control range of 100-140 mg/dL. This rapid fall of glucose levels leads the FUSION system to either start a dextrose infusion if one is not currently infusing, or to rapidly increase the rate of the current dextrose infusion. The FUSION systems glucose control software will also be optimized to decrease the dextrose infusion more quickly in states where the glucose level is in the desired control range and is either stable or increasing. These efforts to avoid excessive use of dextrose should decrease overall fluid intake, as the dextrose infusion accounted for 88% of the total fluid given by the FUSION system.

Finally, the risk of fluid overload will be minimized through routine monitoring of the subjects for signs of fluid overload, throughout the 24-hour closed loop glucose control session. These signs will include evidence of peripheral edema (swollen hands, ankles, legs, eyelids), increased respiratory rate, shortness of breath, or signs of pulmonary edema on exam such as rales. Excessive volume loading, from the FUSION system, will be defined as fluid delivered by the FUSION system (e.g., insulin infusion and dextrose infusion) in excess of 2000 mL during the 24 hour closed loop session. If this fluid delivery threshold is exceeded on a subject, the study will be stopped on that subject.

The benefits of creating a closed loop glucose control system for use in the inpatient setting outweigh the risks of excessive fluid intake in this highly monitored CRC study.

